7.2. Immunogenicity

Blood samples will be collected to examine the formation of antibodies to golimumab at the specified visits as shown in the schedule of events of the protocol. For subjects who discontinue SC study agent administrations, samples will be collected at their 2 months safety follow-up visit. All immunogenicity evaluations will be based on the subjects who receive at least 1 injection of study agent (Safety analysis set).

For the analyses, a subject is included in one and only one treatment group on the basis of the treatment regimen followed. The description of the treatment groups are as follows:

- Golimumab q2w

The data analysis of antibodies to golimumab includes the following:

- The antibody status (positive, negative) of subjects will be summarized by golimumab treatment groups. For subjects who discontinue SC study agent administrations and complete 2 months safety follow-up, a listing of their antibody status will be presented.
- The relationship between antibody to golimumab status and efficacy evaluations will be assessed at Week 52: C-peptide AUC by antibody to golimumab status and treatment group.
- The relationship between antibody to golimumab status and safety will be assessed at Week 52: Injection-site reactions by antibody to golimumab status and treatment group.
- Onset and duration of antibody formation
- Table and figure of serum golimumab concentrations by antibody to golimumab status.

7.3. Pharmacodynamics

Summary statistics of total and free TNF α values and change from baseline will be evaluated. TNF α values below the lower limit of quantification will be treated as zero.

PD Analyses Presentation

PD analyses will be summarized through the Week 52:

For the analyses, a subject is included in one and only one treatment group on the basis of the treatment regimen followed. The description of the treatment groups are as follows:

- Golimumab q2w

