The PK/TE model suggested that an induction dosing regimen of 60 mg/m² SC (to a maximum of 100 mg) at Week 0 and Week 2 followed by a maintenance dosing regimen of 30 mg/m² SC (to a maximum of 50 mg) q2w or 60 mg/m² SC (to a maximum of 100 mg) q4w results in suppression of TNF α to a level approximating that of etanercept. This target would not be achieved with a 30 mg/m² SC q4w dose. The 30 mg/m² q2w and 60 mg/m² q4w maintenance dosing regimens would have the same overall exposure (AUC) and similar TNF α suppression; however, the 60 mg/m² q4w regimen would have higher peak/trough concentration fluctuations and thus more fluctuation on suppression of TNF α . It is known that TNF α has direct cytostatic and cytotoxic effects on β -cells.^{2,58} Thus the TNF α elevations that would be expected to occur during the troughs with the higher, but less frequent dosing, may result in more damage to residual β -cells. As the overall exposure to golimumab with these dosing regimens may be considered equivalent, the 30 mg/m² SC (to a maximum of 50 mg) q2w dosing regimens was preferred due to less peak/trough fluctuation.

3. Comparison of Golimumab Dose Regimens Between the T1D Population with Other Disease Populations of Adults and Children

Population PK simulations were performed comparing the proposed T1D dosing regimen with dosing regimens that have previously been studied in the pediatric populations (pJIA and pediatric UC, [Figure 3](#) Panels A and B, respectively). The simulations to develop this dosing

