9.3. Clinical Pharmacology

9.3.1. Evaluations

Serum samples will be used to evaluate the PK, the immunogenicity of golimumab (antibodies to golimumab), and pharmacodynamics (PD; free/total TNF α). Sera collected may additionally be used to evaluate biomarkers for safety or efficacy aspects to address concerns that may arise during or after the study. Subject confidentiality will be maintained. Sera for the measurement of golimumab concentration, antibodies to golimumab, and free/total TNF α will be derived from the same blood draw.

Instructions for the collection, handling, and shipment of these samples are found in the Laboratory Reference Manual provided by the sponsor.

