7. CLINICAL PHARMACOLOGY

7.1. Pharmacokinetics

Pharmacokinetics (PK) samples for measuring serum golimumab concentrations will be collected from all subjects at the specified visits as shown in the schedule of events of the protocol. All PK evaluations will be based on the subjects who receive at least 1 injection of golimumab (PKE analysis set). No imputation for missing concentration data will be performed.

The data analysis of serum golimumab concentrations includes the following:

- Summary of serum golimumab concentrations at each visit by treatment group
- Summary of serum golimumab concentrations at each visit by age group (≥ 6 to < 12 Years, ≥ 12 to < 21 Years)
- Summary of serum golimumab concentrations by treatment group and by body weight quartiles
- Summary of serum golimumab concentrations by treatment group and by body weight category (< 45 kg, ≥ 45 kg)
- Proportion of subjects without detectable serum golimumab concentration at each visit by treatment group
- Median serum golimumab concentrations plotted over time by treatment group

In addition, the relationship between serum golimumab concentrations, and antibody to golimumab status, safety and efficacy may be explored using graphical displays.

For summary statistics of serum golimumab concentrations, concentration values below the lower limit of quantification will be treated as zero. Once a subject meets one of the following dosing deviation criteria, the subject's data will be excluded from the by-visit data analyses from that point onwards.

Dosing deviation criteria:

- Discontinue SC study agent administration

- Skipped an SC administration
- Received an incomplete/incorrect SC dose
- Received an incorrect SC study agent
- Received and additional SC dose

In addition, if a subject has an administration more than 7 days earlier or later than the scheduled dosing date, the concentration data collected between such a dosing visit and the subsequent dosing visit will be excluded from the by-visit data analyses. For the Week 26 visit, if the PK sampling time deviates more than 3 days earlier or later than the scheduled date, the PK concentration at this visit will be excluded from the by-visit data analyses. Additional exclusions for incongruous PK data to be implemented based on Janssen SOP-07948v2.

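### SAP 7.3 lists only the golimumab group for the TNF-alpha summaries, so their change from baseline has no concurrent control although both arms are scheduled for sampling

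*SAP*

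**What the plan says.** SAP 7.3 (Pharmacodynamics) covers total and free TNF-alpha: "values and change from baseline will be evaluated". TNF-alpha "values below the lower limit of quantification will be treated as zero". The presentation runs through Week 52. The grouping rule reads "For the analyses, a subject is included in one and only one treatment group on the basis of the treatment regimen followed". The next line is in the plural, "The description of the treatment groups are as follows", but one bullet follows: "Golimumab q2w". SAP 7.1 (pharmacokinetics) and SAP 7.2 (immunogenicity) list the same single group.

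On sampling, the Time and Events Schedule for the double-blind period has a free/total TNF-alpha row with no arm restriction. Protocol 9.3.1 takes TNF-alpha from the blood draw used for the other clinical pharmacology measurements (it begins "Sera for the measurement of golimumab concentration, antibodies to golimumab"). SAP 7.1 says of the pharmacokinetic part of that draw that "samples for measuring serum golimumab concentrations will be collected from all subjects at the specified visits".

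On purpose, Protocol 3.2.2 describes a regimen that a model predicted would suppress TNF-alpha "to a level approximating that of etanercept".

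**The concern.** A list with only the active drug suits golimumab concentrations, because placebo subjects have none to summarise. TNF-alpha is endogenous and can be measured in both arms. With golimumab alone, a change from baseline during the year after diagnosis cannot be separated from change that would have occurred anyway. Protocol Section 1 gives a reason to ask: it reports higher serum TNF-alpha in new-onset patients than in those with long-standing disease.

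At stake is how the trial is read. The regimen had not been studied before and was chosen by modelling TNF-alpha suppression. If the primary endpoint is missed, the sponsor will want to know whether the target was suppressed without benefit or was not suppressed. A randomized comparison of TNF-alpha change would inform that, and its control samples are already in the schedule.

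**Working it through.** The plan states no figure for this analysis. Its one design figure, 90% power with 81 subjects, reproduces: the difference is ln(1.635) − ln(1.385) = 0.166 with SD 0.215, and a two-sample t-test with 54 and 27 subjects has power 0.899. Nothing below changes it.

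**Is placebo TNF-alpha sampled?** No sentence says so in those words. It follows from three places:
- the schedule row is not limited by arm;
- Protocol 9.3.1 specifies a shared blood draw;
- SAP 7.1 has pharmacokinetic samples taken from every subject.

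**Is a placebo summary planned elsewhere?**
- Protocol 11 limits the pharmacokinetic and immunogenicity analyses to golimumab recipients. It sets no such limit for pharmacodynamics.
- SAP 5.2.3 asks for summaries in each treatment group, but it belongs to the efficacy section and is not carried into Section 7.
- SAP 7.4 and Protocol 11.7 describe optional plots and modelling, and neither specifies a placebo comparison.

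**How much is left out?** Through Week 52 the row marks Weeks 0, 2, 4, 8, 12, 26, 33, 38, 45 and 52, which is 10 time points. With 27 placebo subjects, 27 × 10 = 270 samples, from 27/81 = 33% of the randomized subjects. This is a ceiling: the schedule's footnote ranks total and free TNF-alpha last when serum is short, and Protocol 9.3.2 makes the assay conditional on volume.

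**What would the control add?** Let τ be the drug effect on mean change and δ the change that would occur without drug.
- Golimumab arm alone: expected change = τ + δ.
- Golimumab minus placebo: (τ + δ) − δ = τ.

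In units of the SD of change, and with complete data, the standard error is √(1/54) = 0.136 for one arm and √(1/54 + 1/27) = 0.236 for the difference. The approximate 95% half-widths (× 1.96) are 0.27 and 0.46. The difference is less precise, but δ is removed.

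**What does the zero rule do?** Let p0 and p1 be the shares below LLOQ at baseline and after dosing. If every such value is replaced by s, the mean change contains the term s × (p1 − p0). The mean change under zero therefore differs from that under s by −s × (p1 − p0). The documents give neither the LLOQ nor the shares. With p0 assumed at 10%, the mean fall is larger under zero by (in LLOQ units):

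| p1 (assumed) | versus LLOQ/2 | versus LLOQ |
|---|---|---|
| 10% | 0 | 0 |
| 30% | 0.10 | 0.20 |
| 50% | 0.20 | 0.40 |
| 80% | 0.35 | 0.70 |

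A simulation with lognormal values (log-scale SD 0.6, assumed) compares each convention with the true mean change, again in LLOQ units:

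| p0, p1 | True | Zero | LLOQ/2 |
|---|---|---|---|
| 10%, 30% | −0.94 | −1.07 | −0.97 |
| 10%, 50% | −1.39 | −1.64 | −1.44 |
| 10%, 80% | −1.86 | −2.22 | −1.87 |
| 30%, 80% | −0.92 | −1.13 | −0.89 |

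In these settings zero overstates the fall by 14% (1.07/0.94) to 23% (1.13/0.92), while LLOQ/2 stays within 0.05 LLOQ of the truth. Protocol 11.4 sets the zero convention for golimumab concentrations and pharmacokinetic parameters. The protocol has no such rule for TNF-alpha.

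**The case against.** The strongest reply is that the single bullet is text carried over from the pharmacokinetics section. It sits under a plural heading, and SAP 2.2.1 makes the full analysis set the default, so placebo subjects are in the population anyway. The carry-over is likely. However, a default population does not override an explicit group list, and a programmer following SAP 7.3 would produce one column.

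Second, a reader might infer that this table is the trial's only check on target suppression and can say nothing about it. The documents do not support that. SAP 7.4 foresees optional plots of golimumab concentration against total and free TNF-alpha, Protocol 11.7 allows exposure-response modelling, and Protocol 9.4 allows circulating cytokines to be assessed. The modelled target was also a level of suppression approximating etanercept, which observed values in treated subjects address in part. What remains is that SAP 7.3 is the only firmly planned summary of TNF-alpha change.

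Third, the natural-course argument has a direction but no size. Protocol Section 1 compares patient groups at different disease stages and gives no first-year trajectory, so any percentage for natural decline would be invented. Slow drift would also affect the Week 2 and Week 4 changes little. Both points stand. They limit the claimed consequence but do not justify leaving out a control that is already scheduled.

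Fourth, TNF-alpha is not among the objectives and endpoints in Protocol 2.1, and no test depends on it. That is correct and keeps the point modest.

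**Conclusion.** The point holds as a cheap improvement to a descriptive analysis. As written, SAP 7.3 gives an uncontrolled change from baseline and leaves up to 270 placebo samples through Week 52 without a planned summary. The bias from omitting placebo equals δ, whose size the documents do not give. The conclusion rests on the inference that placebo TNF-alpha is sampled, which is strong but indirect, and on reading the group list literally.

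The zero rule is a separate and minor matter, and it does not cause the missing control. A reader might infer that it hides suppression, because a subject below LLOQ at baseline cannot show a fall. That is an assay floor, present under any convention. The effect of the rule itself runs the other way when more values are below LLOQ after dosing than at baseline: it enlarges the mean fall. The effect is nil when the shares are equal, and its size here is unknown.

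The primary analysis, alpha and sample size are unaffected.

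**What to change.** In SAP 7.3:
- Add placebo to the group list and name the analysis set.
- Summarise free and total TNF-alpha by arm and visit, as values and as change from baseline.
- Report the golimumab-placebo difference in change from baseline by visit with a 95% confidence interval, labelled descriptive.
- Report the number and proportion below LLOQ by arm and visit, and add medians or an LLOQ/2 sensitivity summary. If more than half the values at a visit are below LLOQ, report the median as below LLOQ.
- Keep subjects whose baseline is below LLOQ. Excluding them selects on a high baseline, invites regression to the mean within each arm and discards data.

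The cost is a few lines of SAP text, one more column in existing tables and, at most, assays on samples already drawn. Visit-level numbers should be shown, because limited sample volume may make the data incomplete.

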7.4. Pharmacokinetic/Pharmacodynamic Relationships

The relationship between serum golimumab and pharmacodynamic markers may be explored. Scatter plots of serum golimumab concentrations versus TNF α (total and free), fasting blood glucose, plasma glucose, HbA1c, insulin and c-peptide may be generated. If PK/PD modeling is performed, the results will be reported in an independent technical report.

REFERENCES

1. Autoimmunity-Blocking Antibody for Tolerance in Recently Diagnosed Type 1 Diabetes (AbATE)
2. Study of Thymoglobulin to Arrest Type 1 Diabetes (START)
3. Inducing Remission in New Onset T1DM with Alefacept (Amevive®) (T1DAL)
4. Seaquist, Elizabeth R et al. “Hypoglycemia and diabetes: a report of a workgroup of the American Diabetes Association and the Endocrine Society.” *Diabetes care* vol. 36,5 (2013): 1384-95. doi:10.2337/dc12-2480
